## **5.5. Potential Benefits**

Each subject enrolled will be aware that the results are likely to provide new insights into the mechanism and eventually treatment and ongoing management of asthma triggered by RV. The benefits of participating in these studies are likely to outweigh any risk from the experimental RV challenges, which have been performed safely at our institution for over 20 years without any serious untoward events.

## **6. Investigational Agent /Device/Intervention**

### **6.1. Investigational Agents/Devices/Interventions**

#### **6.1.1. Investigational Agent #1**

RV-16 (IND #15162)

##### **6.1.1.1 Formulation, Packaging, and Labeling**

The strain of RV that will be used is a pool of RV (strain 16) that will be provided by [name] laboratory at the University of Virginia (UVA). [name], who is the IND-holder for this study, has collaborated with Johnson & Johnson, Inc. to produce this pool of RV under GMP conditions.

A single batch has been manufactured. HRV-16 will be supplied in gamma irradiated polypropylene cryovials containing clarified tissue culture lysate (Eagle's Modified Essential Medium containing 10% [8-12% acceptance criteria] gamma irradiated Fetal Bovine Serum (FBS) derived from animals from a Bovine Spongiform Encephalopathy (BSE) free country [Australia] and certified; final pH 6.5 to 8.5) which has been passed through a 0.2 µm filter, filled into gamma-irradiated polypropylene cryovials, snap frozen, and stored at -60°C or below.

Manufacturer: [name]. University of Virginia School of Medicine. [name]. [name], [name] [name]

The final viral concentration of the cGMP safety tested HRV16 pool is significantly higher than the dose generally used to induce experimental rhinovirus infections.

In advance of a planned inoculation, designated staff at [name] laboratory will prepare in a laminar flow hood a single-use vial containing approximately 300 TCID50 in 1 mL of Lactated Ringer's solution for human use, using aseptic techniques as per the lab's SOP. The actual challenge dose of the virus will be determined by back titration thereby allowing the dilution to be adjusted as necessary to maintain the planned challenge titer should loss of titer occur during storage. The label for the pre-titrated vial dispensed for this study label will include at least the following information:

- RV-16 challenge inoculum dose
- Protocol number
- Investigational use statement
- Date and time prepared

Designated study staff will receive the challenge virus dose which will be transported to the Allergy Research Lab on wet ice using an insulated, closed container with a biohazard label. The vial of inoculum is transferred to a -80° freezer and stored until the day of inoculation. It is then thawed as per the SOP. Once thawed the inoculum must be used promptly (within 4 hours) to insure proper dosage potency, although there is evidence that the virus remains viable, and TCID50 stable, for extended periods when stored at 4°C.

#### **6.1.1.2 Dosage, Preparation, and Administration**

For virus inoculation, each patient will be inoculated with approximately 300 TCID50 after obtaining the pre-virus inoculation nasal wash. Dose selection is described in Section 1.2 (Rationale for Selection of Investigational Product or Intervention)

Approximately 75 TCID50/0.25 ml will be instilled into each nostril during the initial inoculation. Five to 10 minutes after the initial inoculation, another inoculum (using the same amount of RV) will be administered for a total of 1 ml.

## **6.2. Drug Accountability**

Under Title 21 of the Code of Federal Regulations (21CFR §312.62) the investigator will maintain adequate records of the disposition of the investigational agent, including the date and quantity of the drug received, to whom the drug was dispensed (participant-by-participant accounting), and a detailed accounting of any drug accidentally or deliberately destroyed.

Records for receipt, storage, use, and disposition will be maintained by the study site. A drug-dispensing log will be kept current for each participant. This log will contain the identification of each participant and the date and quantity of drug dispensed.

All records regarding the disposition of the investigational product will be available for inspection.

## **6.3. Assessment of Participant Compliance with Investigational Agent**

N/A (single administration under directly-supervised conditions).

## **6.4. Toxicity Prevention and Management**

Toxicity is prevented by selecting well-controlled, mild asthmatics unlikely to experience a severe exacerbation, by having medications on site and at home for management of symptoms, and by daily study visits to the peak of the viral illness.

## **6.5. Premature Discontinuation of Investigational Agent**

N/A (only a single dosing of the RV will be performed on any subject). No subject will be given more than one dose of the product.

## **7. Other Medications**

### **7.1. Concomitant Medications**

#### **7.1.1. Protocol-mandated**

Non investigational drugs that will be available at the clinical site include: Methacholine, oral corticosteroids (prednisone), Albuterol (MDI and nebulizer), and oxymetazoline.

#### **Other permitted concomitant medications**

Albuterol MDI 2 puffs q4h prn.

### **7.2. Prophylactic Medications**

N/A

### **7.3. Prohibited Medications**

Topical (nasal or inhaled) corticosteroids (CCS), oral corticosteroids, leukotriene modifiers, antihistamines, omalizumab, theophylline, short- and long-acting anti-muscarinic agents (LAMAs), long-acting  $\beta$ -agonists (LABAs), cromolyn, and nedocromil.

### **7.4. Rescue Medications**

Albuterol MDI or nebulizer, prednisone

## **8. Study Procedures**

### **8.1. Enrollment**

Potential participants will have had initial screening visits described in the screening study protocol (UVA IRB# 12656 or 19512).

It is anticipated that study participants will be enrolled from UVA, Virginia Commonwealth University, James Madison University, Liberty University, University of Richmond, Mary Baldwin College, Washington and Lee, and other universities located within 90 minutes by car from the UVA campus. Participants will be recruited through the use of posters/flyers, newspaper ads, and internet as well as referrals from other health care professionals.

### **8.2. Visit 1 – Screening/Baseline Visit (Day -7)**

Participants considered for study will have previously participated in the screening protocol within 1 year before Visit 1. Clinical information obtained from the screening protocol may be applied to eligibility as described in Section 4 above, and will be added to the participants' Visit 1 study record.

For this study, all visits will take place at the Clinical Research Unit on the 1st floor of the Medical Center Barringer Wing or at the University Hospital or the Clinical Research Center (CRC) located on the 3rd floor of the University of Virginia Children's Hospital Outpatient Building (Battle Building) in Charlottesville. The baseline visit will take place ~7 days (5-28 days) before RV inoculation visit. The research study will be explained in lay terms to each potential research participant. The potential participant will sign an informed consent form before undergoing any study procedures. Once the informed consent has been signed, the participant is considered enrolled in the (screening) study and will be assigned a unique participant number

The purpose of the baseline visit is to reconfirm eligibility to continue in the study and to perform baseline assessments.

The following procedures, assessments, and laboratory measures will be conducted to confirm participant eligibility and for baseline assessments:

1. Urine pregnancy test for all women of childbearing potential.
2. ACT (asthmatic subjects) – must be  $\geq 20$
3. Blood (10 ml) for viral antibody serology and CBC & differential and 50-ml of blood will be obtained for PBMCs (which can be collected at Visit 2 as long as collection is before inoculation).
4. Spirometry
5. Exhaled nitric oxide (FeNO) on asthmatics only
6. Subjects will be instructed on the use of diary cards, which will be used to record upper and lower respiratory tract symptom scores twice daily, as well as how to use the ATS approved Microlife Electronic PEF and FEV1 monitor and the number of puffs of albuterol required for resolution of symptoms.
7. If required, subjects will also be given an albuterol inhaler (MDI) to use as a rescue medicine as needed.
8. Baseline assessment of past medical history. An additional targeted medical history of acute events over the last month will be obtained to use in our assessment of adverse events.
9. A limited physical examination will be performed including chest auscultation.
10. Vital Signs (blood pressure, heart rate, temperature, height, weight)
11. Methacholine challenge (not to be performed if results were obtained within the past year in the separate screening protocol)
12. Between visit 1 and 2 subjects will fill out diary cards weekly.

Visit 1 can be completed in multiple visits if they occur within the visit window.

### **Study Visit 2 - Inoculation (Day 0)**

1. Urine pregnancy test for all women of childbearing potential.
2. Vital Signs (blood pressure, heart rate, temperature, height, weight)
3. Prior to inoculation asthma control will be confirmed by the following means -
  - a. Diary cards will be reviewed
  - b. AEs review
  - c. Spirometry – Must demonstrate normal lung function (FEV1 > 70% predicted or FEV1/FVC ratio > 75% for subjects with FVC values between 80 and 87% predicted whose FEV1 values fall below 70%).
  - d. A limited physical examination will be performed including chest auscultation
4. Nasal scraping
5. Nasal wash / sponge

6. Blood draw – 50mls of blood will be obtained for PBMCs ONLY if not collected at Visit 1
7. Exhaled nitric oxide (FeNO) on asthmatics only
8. Inoculation of subjects with RV-16

Continued eligibility must be confirmed during the initial part of this study visit. Sample collection and the inoculation may be delayed if a subject is ill or has evidence of loss of asthma control. The inoculation will not occur if the upper airway modified Jackson criteria symptom scores are  $\geq 7$ . The participant may be brought back to continue the Day 0 visit. Procedures completed may be repeated to confirm the subject's eligibility. The repeat visit must occur within the stated visit window from Visit 1.

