	
and/or allergic conjunctivitis on natural exposure to relevant allergens.
 
10. Negative methacholine challenge (less than 20% decline in FEV1 at <math>\leq 8</math>mg/ml) within 1 year
 
11. FEV1 <math>\geq 70\%</math> predicted or FEV1/FVC <math>\geq 80\%</math>.
 
12. No history of wheezing with viral infection in the last 6 years, and no use of rescue inhalers or long-term controllers for asthma in the last 6 years.
 
Allergic Asthmatic Subjects
 
13. Allergy as determined by <math>\geq 1</math> positive prick skin test (wheal <math>\geq 5</math> mm diameter and 3mm larger than the diluent control) to Virginia inhalant panel. Subjects are not required to have allergy symptoms at the time of study. Subjects will report history of symptoms of sneezing, rhinorrhea, pruritus, nasal congestion, and/or allergic conjunctivitis on natural exposure to relevant allergens.
 
14. Asthma determined by physician diagnosis and by a positive methacholine challenge (at least 20% fall in FEV1 at a methacholine concentration of <math>\leq 16</math> mg/ml) at screening protocol visit before enrollment (obtained within the past year).
 
15. Asthma must be controlled as determined by ACT score <math>\geq 20</math> and normal lung function (FEV1 <math>\geq 80\%</math> predicted and FEV1/FVC ratio <math>> 0.65</math>).

Exclusion Criteria (all subjects)
	
 
1. Positive test for serum neutralizing antibody to RV16 at enrollment visit (<math>\geq 1:8</math>) (Visit 1).
 
2. Upper airway modified Jackson criteria symptom scores <math>\geq 7</math> at time of inoculation.
 
3. Chronic heart disease including bradycardia, lung diseases other than asthma, or other chronic illnesses including epilepsy, peptic ulcer disease, thyroid disease, urinary tract infection, vagotonia, autoimmune disease, primary or secondary immunodeficiency or any household contacts who are known to be immune deficient. Any medical conditions that could be adversely affected by the administration of cholinergic agent.
 
4. Any use of LT modifiers, omalizumab, nasal corticosteroids within 4 weeks prior to Visit 1.
 

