1. Allergy as determined by  $\geq 1$  positive prick skin test (wheal  $\geq 5$  mm diameter and 3mm larger than the diluent control) to Virginia inhalant panel with 5 years (done as part of screening protocol). Subjects are not required to have allergy symptoms at the time of study. Subjects will report history of symptoms of sneezing, rhinorrhea, pruritus, nasal congestion, and/or allergic conjunctivitis on natural exposure to relevant allergens.
2. Asthma determined by physician diagnosis and by a positive methacholine challenge (at least 20% fall in FEV1 at a methacholine concentration of  $\leq 16$  mg/ml) at screening protocol visit before enrollment (obtained within the past year).
3. Asthma must be controlled as determined by ACT score  $\geq 20$  at Visit 1 and normal lung function (FEV1  $\geq 80\%$  predicted and FEV1/FVC ratio  $>0.65$ ).

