**Study therapy regimen:**

- Rhinovirus-16 administration  
Rhinovirus infection is expected to result in cold symptoms among all subjects, and mild asthma symptoms among the asthmatic cohort. In addition, neutropenia and lymphopenia are expected within the first week after rhinovirus inoculation without clinical consequence. Upper and lower respiratory symptom data will be recorded on the RV Dairy Symptom Cards completed by study participants. An adverse event will be recorded in the following circumstances –
  - Treatment with an antibiotic or inhaled or systemic corticosteroid
  - Drop in lung function to  $\leq 70\%$  of predicted or ACT score  $< 19$
  - Febrile Neutropenia (ANC  $< 1000/\mu\text{L}$  with a single temperature of  $> 38.3$  degrees C (101 degrees F) or a sustained temperature of  $\geq 38$  degrees C (100.4 degrees F) for more than one hour)
  - Lymphopenia (ALC  $< 800/\mu\text{L}$ )
  - Any cytopenia with appropriate associated symptoms

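### Unless the entry limits are re-tested on day 0, the pre-inoculation spirometry check can pass an asthmatic whose FEV1 is below the protocol's own limit for controlled asthma

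*Combined protocol and SAP*

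**What the plan says.** The synopsis lists controlled asthma as an inclusion criterion for the asthma cohort: "Asthma must be controlled as determined by ACT score" of at least 20, together with FEV1 at least 80% predicted and FEV1/FVC above 0.65. Section 4.2 repeats this with a visit attached to the ACT score: "at Visit 1 and normal lung function", followed by the same two spirometry limits.

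On the dosing day, item 3 of Study Visit 2 opens with "Prior to inoculation asthma control will be confirmed by the following means". It lists diary review, adverse-event review, spirometry and a limited examination. The spirometry item, 3c, reads "Must demonstrate normal lung function (FEV1 > 70% predicted or FEV1/FVC ratio > 75% for subjects with FVC values between 80 and 87% predicted", and the sentence ends by restricting the ratio route to subjects with FEV1 under 70%.

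The same visit adds "Continued eligibility must be confirmed during the initial part of this study visit", without naming the criteria. It allows a delay for illness or lost asthma control. It also sets one symptom cut-off: "The inoculation will not occur if the upper airway modified Jackson criteria symptom scores are" 7 or more.

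Section 12.2.1 lists, among the events to be recorded as adverse events after inoculation, "Drop in lung function to" 70% of predicted or less.

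**The concern.** Two parts of the protocol use one term, for one purpose, with different numbers. Section 4.2 uses it to define controlled asthma, and item 3c uses it to confirm asthma control just before live virus is given. The dosing-day version is the looser one. It drops the FEV1 limit from 80% to 70%, omits the ratio limit on its main route, and adds a second route for subjects below 70%.

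Section 6.4 relies on choosing mild, well-controlled asthmatics to prevent toxicity. Staff who work from the Visit 2 list alone could inoculate an asthmatic who does not meet the protocol's own definition of control that day. Through the second route, that subject could already be at the level section 12.2.1 treats as an adverse event.

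**Working it through.** The plan gives no calculated figure to reproduce, so the check compares the rules and tests whether the looser routes can be reached in practice.

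**Inputs**

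| Rule | FEV1, % predicted | FEV1/FVC | Other |
|---|---|---|---|
| 4.2 and synopsis, asthmatics | ≥80 | >0.65 | both required |
| Item 3c, route A | >70 | none | – |
| Item 3c, route B | <70 | >0.75 | FVC 80–87% predicted |
| 12.2.1 adverse event | ≤70 | – | lung function read as FEV1 (assumption) |

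The documents give no predicted FEV1/FVC ratio. I assume 0.82 to 0.88 in step 2 and 0.86 to 0.90 for the example in step 3.

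**Step 1. FEV1 alone.** Any asthmatic with FEV1 above 70% and below 80% predicted passes route A and fails section 4.2, whatever the ratio. This needs no assumption.

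**Step 2. The missing ratio condition.** FEV1 % predicted = FVC % predicted × actual ratio ÷ predicted ratio. Take FVC at 100% predicted and an actual ratio of 0.65, which fails the 4.2 ratio limit:

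- predicted ratio 0.82: 65 / 0.82 = 79.3%
- predicted ratio 0.85: 65 / 0.85 = 76.5%
- predicted ratio 0.88: 65 / 0.88 = 73.9%

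All three pass route A and fail both 4.2 limits. In the other direction, FEV1 of 70.1% with FVC of 100% passes route A at an actual ratio of 0.701 × 0.82 = 0.575 to 0.701 × 0.88 = 0.617. An ordinary FVC is enough. These subjects also fail the FEV1 limit, so the FEV1 difference in step 1 is the main one.

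**Step 3. The sub-70% route.** Route B needs an actual ratio above 0.75 with FEV1 under 70%. The predicted ratio must therefore exceed 0.75 × FVC % ÷ 70:

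- FVC 80%: 0.75 × 80 / 70 = 0.857
- FVC 87%: 0.75 × 87 / 70 = 0.932

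Below a predicted ratio of 0.857 nobody can use route B, so it is narrow. Where it can be used, at FVC 80% the lowest FEV1 admitted is about 60 / 0.86 = 69.8% to 60 / 0.90 = 66.7%, with 60 = 0.75 × 80. Everyone it admits is below 70% by construction, hence at the adverse-event level before inoculation.

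**Step 4. Which rule governs.**

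- *Section 4.2 is re-tested on day 0.* Both rules bind. FEV1 of at least 80% already implies more than 70%, so item 3c does nothing for asthmatics and there is no gap.
- *Section 4.2 applies at entry only.* Item 3c is the operative limit, and steps 1 to 3 describe who can be inoculated.

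The text does not settle this. Section 4.2 ties Visit 1 to the ACT score but gives no clear visit for the spirometry values. The Visit 1 list in section 8.2 repeats the ACT limit but gives spirometry no threshold. No section states an order of precedence.

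**The case against.** The strongest reply is that these are two checks at two times. Section 4.2 governs enrolment, Visit 1 reconfirms eligibility, and item 3c is a looser same-day go/no-go test, which is an ordinary design. The 70% figure also appears in the allergic rhinitis entry criterion, and the Visit 2 list serves all three cohorts, so it may simply be a common floor. Item 3 also requires diary review, adverse-event review and auscultation. Inoculation may be delayed for lost asthma control, exclusion 16 gives the investigator discretion, and spirometry is repeated on days 1 to 4. The sub-70% route demands a stricter ratio (above 75%) than section 4.2. Nothing in the documents links a day 0 FEV1 of 71–79% to harm.

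Most of this stands. A deliberate tolerance is possible, and the safeguards are real. But the delay is discretionary, and item 3 says its purpose is to confirm asthma control while using a number below the protocol's definition of it. A common floor does not explain why a subject already below 70% should be inoculated.

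A reader might go further and treat the distance from the day 0 FEV1 to 70% predicted as a lost safety margin. The documents do not support that. The 70% level in section 12.2.1 is a recording rule. Treatment in Appendix 1 is triggered by falls of 20–29%, 30–49% and 50% or more from baseline, and the stopping rules in 11.2 and 11.5 contain no percent-predicted limit.

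**Conclusion.** The point holds as a minor one, on the reading that section 4.2 is not re-tested on day 0. On that reading item 3c permits inoculation of an asthmatic at 71–79% predicted with no ratio condition. More rarely it permits one below 70%, and only if the predicted ratio exceeds 0.857. The first statement follows from the text alone. The ratio and sub-70% examples rest on the assumed predicted ratios, and the adverse-event comparison rests on reading lung function in section 12.2.1 as FEV1.

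A reader might infer that the protocol contradicts itself or directs staff to inoculate uncontrolled asthmatics. It does neither, because the continued-eligibility sentence can be read so that both limits bind. The documents give no within-subject FEV1 variability, so the number of asthmatics affected is unknown. No endpoint, power or alpha figure changes.

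**What to change.** In item 3c, require asthmatics to meet the section 4.2 limits on day 0: FEV1 at least 80% predicted and FEV1/FVC above 0.65. At minimum, remove the sub-70% route for them. If the limits are missed, use the repeat visit already provided for: "The repeat visit must occur within the stated visit window from Visit 1". Leave the present limit for allergic rhinitis and healthy controls. If a lower same-day floor for asthmatics is intended, state that it replaces section 4.2 on day 0.

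The change is one of wording. Spirometry is already done on day 0 and is listed before the nasal samples. With Visit 1 at the nominal 7 days before inoculation, 28 − 7 = 21 days of the 5–28 day window remain for a repeat; a first attempt on day 28 leaves none. A repeat more than 72 hours after the CoVID-19 test needs a new test. The downside is a few delayed or lost asthma inoculations, a number the documents do not allow one to estimate. Section 11.3 provides for replacement, so the cost is enrolment time rather than sample size.

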### **Study Visit 3, 4, and 5 (Day 1, 2, and 3)**

1. Diary cards will be reviewed for symptom control and AEs.
2. A limited physical examination will be performed including chest auscultation and temperature
3. Nasal scraping
4. Nasal wash / sponge
5. Spirometry
6. Exhaled nitric oxide (FeNO) on asthmatics only

### **Study Visit 6 (Day 4)**

1. Urine pregnancy test for all women of childbearing potential.
2. Diary cards will be reviewed for symptom control and AEs.
3. A limited physical examination will be performed including chest auscultation and temperature
4. Nasal scraping
5. Nasal wash / sponge
6. Spirometry
7. Exhaled nitric oxide (FeNO) on asthmatics only
8. Blood sample (50-ml) will be obtained for AEC (part of the CBC & differential) and for collection of PBMCs for later assessment of Th2-immune deviating capacity of nasal secretions.
9. Nasal biopsies will be obtained
10. Methacholine Challenge

### **Between Visits 6 and 7 (Days 5 and 6)**

Subjects will complete the diary card daily

### **Study Visit 7 (Day 7)**

1. Urine pregnancy test for all women of childbearing potential.
2. Diary cards will be reviewed for symptom control and AEs.
3. A limited physical examination will be performed including chest auscultation and temperature
4. Nasal scraping
5. Nasal wash / sponge
6. Spirometry

7. Exhaled nitric oxide (FeNO) on asthmatics only

